**1. Title of Investigation**

The Effects of Hyperbaric Oxygen on Rheumatoid Arthritis: a Pilot Study.

**4. Purpose of Investigation**

This is a pilot study. The purpose of this investigation is to determine the effects and feasibility of using hyperbaric oxygen therapy (HBO2) for the treatment of rheumatoid arthritis joint pain and prevention of disease progression. In this study it is our intention to not only evaluate effects and feasibility but time, cost, adverse events and effect size in an attempt to predict an appropriate sample size and improve on the study design prior to a more extensive study.

**5. Category of Study and Risk Assessment**

**5.1. Category of Study**

Pilot Study. Hyperbaric oxygen is not an established treatment for rheumatoid arthritis.

Medical Utilization  Prevention  Medical Readiness  Diagnosis/Treatment/Other

**5.2. Proposed Risk:**

Minimal Risk  
 Greater Than Minimal Risk

**6. Proposed Research**

**6.1. Background and Review of Literature:**

Rheumatoid arthritis (RA) is a chronic, systemic, inflammatory disorder of unknown etiology that primarily involves synovial joints, typically symmetrically. If untreated and/or uncontrolled, joint destruction due to erosion of cartilage and bone can cause joint destruction, joint deformities, loss of physical function, severe disability, and difficulties maintaining employment. ACR/EULAR 2010 classification criteria is a score-based algorithm which adds scores of four categories including, joint involvement, serology, acute-phase reactants and duration of symptoms. A score of >6/10 is needed for classification of a patient as having definite RA.

Non-pharmacologic and supplementary therapies include patient education, rest, exercise, nutrition counseling, cardiovascular disease risk reduction, and immunizations to decrease risk of infectious complications of immunosuppression. These are important in the comprehensive management of RA in all stages of disease and are used in addition to drug therapy. Pharmacologic therapies typically start with a disease-modifying antirheumatic drug (DMARD), preferably as soon as possible after diagnosis. DMARDs are commonly used in combination with anti-inflammatory drugs such as nonsteroidal anti-inflammatory

**For Protocol Office use only:**

Protocol title: The Effects of Hyperbaric Oxygen on  
Rheumatoid Arthritis: a Pilot Study.  
FDG20160004H wAMD13

investigator name redacted 28 Jan 20

DGMC Human Research Protocol Template

drugs (NSAIDs) and glucocorticoids which are often used as bridging therapies until the DMARDs become effective. The goal is disease remission. To assess response, disease activity scores are used along with inflammatory markers

### **Literature Review**

There is a paucity of information about the effects of HBO2 on patients with RA in the medical literature. A 1988 letter to the editor in the British Journal of Rheumatology reported ten patients with active classic or definite RA. Eight patients received ten HBO2 treatments at 2 ATA X 90 minutes on alternate days over a 21-day period. Two patients received 'sham' treatment breathing air at normal atmospheric pressure. Clinical assessments were made at -1, 0, 3 (end of treatment period), six and 12 weeks, and included duration of morning stiffness, grip strength, articular index and visual analogue pain scale. Lab indices included hemoglobin, platelet count and ESR. Rheumatoid factor (RF) was measured at times zero, three, and six weeks. The two pre-treatment assessments defined the range for each individual, and subsequent assessments were recorded as improved (+1), in range (0), or worse (-1). The authors concluded that there was a trend toward improvement in HBO2-treated patients. They concluded that the improvement was to be expected if active RA patients are recruited, and noted a similar trend in the sham-treated group. No patients went into remission, and the Rheumatoid Factor did not significantly change. The authors felt that their pilot study failed to demonstrate any therapeutic advantage of HBO2, and further trials were not justified. Weaknesses in this pilot study include small numbers of patients, likely sub-optimal course, frequency of HBO2 therapy and lack of utility of RF to measure disease activity. Larger differences in outcomes between the active and sham groups might have been realized if there were more patients enrolled for a longer, daily treatment course, and a more robust data analysis.

In a 1990 abstract authors reported on their experience treating 50 RA patients with 12 sessions of HBO2 at 1.7 ATA for 40 minutes. All patients had been previously treated with prolonged traditional drug therapy with minor success. The authors reported good immediate and remote clinical results, the best, in patients with systemic manifestations. After HBO2, there were no changes reported in humoral immunity (IgA, IgM or IgG), but serum immune complexes decreased significantly, absolute and relative quantities of T- and B-lymphocytes approached normal levels, and the ratio of theophylline-resistant to theophylline-sensitive lymphocytes decreased significantly. The authors concluded that the beneficial effects of HBO2 on the immune system of the patients was related to intensification of the suppressive function of T-lymphocytes, normalization of cell-bound immunity and decreasing the serum concentration of immune complexes.

A 2002 Russian article reported on 46 patients with rheumatoid arthritis (RA) and 18 with osteoarthritis (OA), all treated with 3.6-4 cGy radiotherapy (RT). Twenty-four of the RA, and ten of the OA patients were treated with a combination of oxygen barotherapy (OBT) consisting of 9-11 sessions at 1.4 bar (1.45 atmospheres absolute) for 40 minutes each, and RT to allow for optimal results from this complex therapy while reducing the known adverse effects of radiation. In the two years that followed, basic clinical assessments included the Ritchie articular index, total pain index, local articular index, pain index for knee and hand joints, circumference of knee and wrist joints, and ultrasound

measuring the magnitude of exudate, erosive processes, osteophytes, articular fissure stenosis, and the thickness of the synovial membrane and cartilage.

Joints irradiation after the oxygen barotherapy (OBT) session was associated with a more pronounced positive effect than RT alone, including significant positive findings in the Ritchie articular index, general pain index, and pain index of the knee joints.

For RA patients, ultrasonic investigations of knee joints revealed negative correlations between treatment effectiveness and synovial membrane thickness ( $r = -0.65$ ,  $p < 0.01$ ), and severity of effusion ( $r = -0.71$ ,  $p < 0.01$ ) for RA patients. For group three OA patients, there was no evidence of cartilage thinning throughout the observation period; progression was found in group 4 ( $r = -0.83$ ,  $p < 0.01$ ). Therapies for all groups were more effective in the early stages of the disease and the best outcomes were found in OA patients.

Although this study evaluated the combination of OBT with radiation therapy for RA and OA patients, and found statistically significant improvement in indices of pain and disease progression, it raises the question of whether there is potential benefit from the use of OBT (hyperbaric oxygen) alone. This is especially true since OBT was at only the equivalent of 1.45 ATA for a total of 9-11 sessions, considering that most OBT sessions in the US are provided at 2 to 2.5 ATA, typically for more than ten sessions.

## **6.2. Relevance/Significance:**

If hyperbaric oxygen consistently relieved the joint pain and stiffness associated with RA, led to an increase in exercise tolerance, activity level and sleep quality, and modified disease progression, there could be a significant role for the use of HBO2 as an adjunct to current therapies, and could reduce the amount of DMARD or Biologic therapy. This would be especially true for patients targeted as possible study participants: 1) those that prefer not to be on the standard rheumatologic medications, 2) those with contraindications to the standard rheumatologic medications, and 3) those that have failed or have incomplete response to standard rheumatologic medications.

## **6.3. Hypotheses or Research Questions or Objectives:**

Proposed primary outcomes:

1. Subjective relief of joint pain, stiffness, and increased activity levels as assessed by the study rheumatologist as measured by disease activity monitoring score (DAS28) and ACR20 criteria.
2. Improved sleep quality to be tracked separately by a sleep quality questionnaire.
3. Subjective improvement in movement and activities of daily living using the RAPID 3.
4. Visual Analog Scale (VAS) for pain to assess changes in subjective pain.
5. Altering the progression of joint disease as measured by ultrasound and MRI measured at baseline, three months, six months.
6. Changes in inflammatory markers as measured by C-reactive protein (CRP) and erythrocyte sedimentation rate (ESR) to be performed at baseline, during HBO2 treatments if subject reports pain relief (defined as improvement of pain of > 40% or zero pain) based on pain assessment (numerical pain scale of 1-10 reported verbally) at

**For Protocol Office use only:**

Protocol title: The Effects of Hyperbaric Oxygen on  
Rheumatoid Arthritis: a Pilot Study.  
FDG20160004H wAMD13

investigator name redacted 28 Jan 20

DGMC Human Research Protocol Template

each hyperbaric treatment visit, at the completion of HBO2 treatments, at three months and six months.

A research lab sample for analysis of Microparticles, neutrophil and platelet activation  will be collected with each CRP/ESR. Microparticles represent a heterogeneous population of vesicles with a diameter of 100 to 1000 nm that are released by budding of the plasma membrane and express antigens specific to their parental cells. Although microparticle formation represents a physiological phenomenon, a multitude of pathologies are associated with a considerable increase in circulating microparticles, including inflammatory and autoimmune diseases, atherosclerosis and malignancies.

#### **6.4. Research Design and Methods:**

HBO2 can be administered either in the multiplace chamber, or the monoplace chamber. The multiplace chamber is compressed with air, and the patients breathe oxygen through hoods or masks. The monoplace chamber is pressurized with oxygen, so that the patient breathes the ambient oxygen. Only the delivery system is different. There is no difference in the oxygen delivered, or in attendant risks.

This is a pilot study.

1. Patient eligibility will be determined by the Rheumatologists, specialists in diagnosing rheumatoid arthritis. Recruitment will take place from their pool of patients. Additionally, patients that have been seen in the military treatment facility (MTF) within the past year with a diagnosis of rheumatoid arthritis will be contacted, after obtaining IRB-approval with a HIPAA waiver. Patients will be recruited if they: diagnosed with rheumatoid arthritis meeting ACR/EULAR 2010 classification criteria and any one of the following:
  - a. Patient does not want to be on rheumatologic medications.
  - b. Patient has contraindications to standard rheumatologic medications.
  - c. Patient has failed treatment or an incomplete response with standard rheumatologic medications.
2. The initial screening visit after the rheumatologist has discussed the trial will be the consenting and review of the inclusion/exclusion criteria. After the consent is signed the Hyperbaric physician will do a physical examination, review of inclusion and exclusion criteria and medication review to determine if it is safe for the subject to receive HBO2. An HCG by point of care testing (POCT) will be completed by the coordinator in women capable of pregnancy. After this exam is done the subject will be scheduled for a trial hyperbaric session.
3. The visit window timeline for screening, Baseline, and first HBO2 treatment to occur all within one month (four weeks) before start of HBO Hyperbaric Therapy Session.
4. **Baseline** The Baseline date is dive #1 date. This visit includes:
  - A visit with the rheumatologist to do routine assessments to establish baseline measurement using the the Disease Activity Scale (DAS28)
  - Labs (CRP and ESR, Basic Metabolic Panel (BMP) and Microparticles) will be done. A MRI with and without contrast and ultrasound will be done on both hands

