**For Protocol Office use only:**

Protocol title: The Effects of Hyperbaric Oxygen on  
Rheumatoid Arthritis: a Pilot Study.  
FDG20160004H wAMD13

investigator name redacted 28 Jan 20

DGMC Human Research Protocol Template

from wrists to proximal phalanges. BMP is done pre-MRI to guarantee adequate kidney function.

- Subjective patient reporting will be captured using the RAPID 3.
  - Sleep quality will be tracked using the Pain and Sleep Quality Questionnaire (PSQ-3).
  - Visual Analog Score for Pain (VAS) will be tracked.
  - Surveys will be administered by a study team member.
5. The subject at this time will be scheduled to start HBO2 treatments. Screening, baseline , first HBO2 treatment all in one month.
6. **During the period that the HBO2 treatments** are taking place the hyperbaric physicians will continue to monitor the subjects and if there is any concern regarding their physical condition they will consult with one of the rheumatologists. Participants will complete 30 sessions within 10 weeks.
7. If the subject reports pain relief, as defined as improvement of pain of > 40% or zero pain, during the HBO2 treatments they will be referred to the rheumatologist for assessment. Pain improvement will be based on a pain assessment (numerical pain scale of 1-10 reported verbally) at hyperbaric treatment visits. Labs (CPR, ESR and Microparticles) will be drawn at this time. RAPID 3 and PSQ-3 and VAS will be done at least six times while undergoing hyperbaric treatments to track subject progress. Labs (CRP, ESR and Microparticles) will be repeated at the conclusion of the HBO2 treatments.
8. At the **month three visit** (+/- 2 window) the subject will see the rheumatologist to track disease activity using the DAS-28. The date of the three month visit will be scheduled for three months from the Baseline visit. The Rheumatologist will order the MRI Ultrasound, and lab studies prior to the three month visit. RAPID 3, PSQ-3 and VAS for pain will be administered at this time. Laboratory samples will be collected prior to the Rheumatology appointment.

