**Study Visits**

	Screening Visit (maybe split into 2 visits) ***	Base line Visit ***	HBO TX ***	Pain relief during HBOT	Compl etion of HBOT	Mo 3 (+/- 2 weeks)	Mo 6 (+/- 2 weeks)
--	--	--	---------------------------	--	------------------------------------	-----------------------------------	-----------------------------------

ICD/ HIPAA	X						
Inclusion/ Exclusion Criteria	X						
Exam by Hyperbaric Physician	X						
Trial HBOT	X						
Hyperbaric treatments			X 30 * **				
Rheumatology Visit		X		X		X	X
Labs		X		X	X	X	X
Ultrasound		X				X	X
MRI		X				X	X
DAS 28		X		X		X	X
RAPID 3		X	X ****	X		X	X
PSQ 3		X	X ****	X		X	X
VAS Pain		X	X *****	X		X	X

\*When subject reports pain relief during HBOT they will be assessed by Rheumatologist.

\*\* Complete 30 HBO treatments within 10 weeks.

\*\*\* Screening, Baseline, First HBOT treatment all within one month (four weeks)

\*\*\*\* at least 6 times while undergoing hyperbaric treatments

The optimal dose response of RA patients to HBO2 is unknown. Modest benefit has been shown in prior studies at 2 ATA and 1.5 bar for 10 and 9-11 sessions, respectively. The subject will be compressed with air in the hyperbaric chamber to 2.0 ATA, and then placed on 100% oxygen by a head tent or mask, for 90 minutes. After hood removal, the chamber is decompressed while the patient breathes chamber air. Treatments are daily, Monday through Friday for a planned total of 30 sessions. Time to change in subjective study outcomes (relief of joint pain, stiffness, improvement in sleep patterns, and increase in activity level) will be documented. Treatments will stop at the end of 30 sessions whether or not there is subjective improvement. After the initial assessment, follow-up with the rheumatologist is scheduled at three and six months which is standard of care for rheumatology patients. If the participant

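### The only pregnancy test named is at screening, up to four weeks before the first HBO2 treatment; repeating it on the dive #1 date would be a cheap improvement

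*Combined protocol and SAP*

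**What the plan says.** Section 6.4, item 2 describes the screening visit: consent, review of eligibility, an examination by the hyperbaric physician, and then the one pregnancy test that the protocol names: "An HCG by point of care testing (POCT) will be completed by the coordinator in women capable of pregnancy". The next sentence reads "After this exam is done the subject will be scheduled for a trial hyperbaric session".

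Item 3 sets the window. Screening, baseline and the first treatment are "to occur all within one month (four weeks) before start of HBO Hyperbaric Therapy Session". Item 5 and a footnote to the Study Visits table repeat the four-week limit.

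Later laboratory work is itemised at three points in section 6.4:
- Baseline (item 4): "Labs (CRP and ESR, Basic Metabolic Panel (BMP) and Microparticles) will be done".
- Pain relief during treatment (item 7): "Labs (CPR, ESR and Microparticles) will be drawn at this time" (the first abbreviation is evidently CRP).
- End of treatment (item 7): "Labs (CRP, ESR and Microparticles) will be repeated at the conclusion of the HBO2 treatments".

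Section 6.6 requires a negative pregnancy test, without giving its timing, and current reliable contraception (inclusion criterion 4). It excludes women who are pregnant, breast feeding or planning pregnancy during the study (exclusion criterion 13).

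**The concern.** The sponsor treats pregnancy as a bar to this treatment. The HCG sits in the same step as the physician's review of whether hyperbaric oxygen is safe for the subject. The bar concerns exposure, but the test that enforces it may come four weeks before the treatment course starts. A conception too recent for the screening test to show, or one after that test, would meet no named test before dive #1. What is at stake is participant safety, not the analysis.

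The plan handles the neighbouring exclusion differently. Exclusion criterion 12 concerns renal insufficiency, and section 6.4 does not leave it to the screening review: a metabolic panel is run before the MRI to check kidney function. Pregnancy gets no comparable recheck in the text available.

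**Working it through.** There is no plan figure to reproduce. The check reads the schedule for every pregnancy test and then measures the longest gap.

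**1. Tests named.** Section 6.4, item 2 gives one HCG, at screening. The baseline labs are CRP, ESR, metabolic panel and microparticles. The labs at pain relief and at the end of treatment are CRP, ESR and microparticles. None includes HCG. Months 3 and 6 (items 8 and 9) mention laboratory work without listing it, so they show nothing either way. Named tests: 1. Named repeats before the course: 0.

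**2. Eligibility review.** Item 2 and the Study Visits table place the inclusion and exclusion review at screening only, so no later review is shown that would bring criterion 13 up again.

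**3. Longest gap to the first treatment of the course.** Item 3 gives 4 weeks. With the proposed repeat on the dive #1 date, the gap becomes 0 days.

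**4. Gap to the baseline contrast MRI.** Item 4 equates the baseline date with dive #1. After the baseline procedures, however, item 5 says "The subject at this time will be scheduled to start HBO2 treatments", so the MRI may fall on an earlier day. On either reading it lies within the same window, up to 4 weeks after the screening test. A dive #1 test would precede the MRI only if both fall on the same day and the test is done first.

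**5. What the tables can show.** The Study Visits table, the source-material table in section 6.8 and the lab-support table in section 11 have no HCG entry even for screening. Their silence is therefore not evidence that a repeat is absent. The finding rests on the itemised narrative.

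**6. Extra tests.** Section 6.6 caps recruitment at 20. Taking the extreme case that all 20 are women who could be pregnant:
- MRI and dive #1 on the same day: 1 × 20 = 20 tests.
- MRI on an earlier day and not covered by Attachment 11: 2 × 20 = 40 tests.

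**The case against.** The strongest reply is that a single test is a deliberate and layered choice. A negative result, required contraception, exclusion of intended pregnancy and a four-week cap all apply before treatment. The Incidental Findings text in section 6.7 adds a full history and examination by a rheumatologist at the start and shorter ones at each later visit. Section 6.4 has hyperbaric physicians seeing participants five days a week, and section 6.7 allows laboratory studies as needed. All of this stands as mitigation. None of it names a pregnancy test at the start of the course.

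Attachment 11 and the consent form are not shown and may contain a check. That is a fair reason to make the MRI test conditional. It has less force for dive #1, because nothing shown extends an MRI form to the hyperbaric sessions.

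A repeat test can also miss a very recent conception. True: it shortens the blind interval but does not remove it.

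A reader might infer stronger versions, which the documents do not support:
- **A 14-week gap to the last session (4 + 10).** This assumes that the ten-week treatment limit runs from dive #1, which is not stated. At the planned five sessions a week the figure is 4 + 30/5 = 10 weeks. Nor would a dive #1 test close that interval, so it cannot be the argument for one.
- **Untested contrast MRIs at months 3 and 6.** Contrast is explicit in the schedule only at baseline, and the later lab work is unspecified.
- **An untested trial session.** The screening column is headed "Screening Visit (maybe split into 2 visits", so the HCG and the trial session may fall on different days. Item 2 nevertheless lists the HCG before the sentence that schedules the trial session, so a same-day rule would be a preference only.

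**Conclusion.** The point holds in a limited form. In the text available, one HCG is named, at screening, and at the start of the 30-session course it may be up to four weeks old. Criterion 13 is then not verified by test at that moment. Four weeks is the maximum that item 3 allows, not a typical value.

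This is a cheap improvement to a safety check. It is not an error in the plan, since nothing in the text promises a repeat or contradicts a single test. The size of the risk cannot be stated: the documents give no pregnancy rate, no fetal-risk figure and no number of women concerned. The conclusion assumes that the unseen attachments do not already require a test on the dive #1 date.

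**What to change.** In women who could be pregnant:
1. Repeat the point-of-care HCG on the dive #1 date, before the session.
2. If the baseline contrast MRI is done on an earlier day, and Attachment 11 does not already cover pregnancy, also test before that MRI, alongside the metabolic panel already drawn for it.
3. Add an HCG row to the Study Visits table, marked at screening and at dive #1.

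The sponsor's clinicians should also state what follows a positive result.

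The cost is one extra test per woman concerned, or two under item 2. It falls at visits already scheduled and can be run by the coordinator who does the screening test. The protocol needs one table row and a short amendment.
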